## **8.4. Exploratory Efficacy Analyses (Not from HRCT Analyses)**

### **8.4.1. Endpoint / Variables**

Additional exploratory endpoints include the severity of index exacerbation, where exacerbations requiring hospitalisations are defined as severe and those not requiring hospitalisation are defined as moderate.

### **8.4.2. Summary Measure**

For the severity of index exacerbation, a summary table detailing the number and percentage of subjects who had moderate or severe index exacerbations. Note: exacerbations requiring hospitalisations are defined as severe and those not requiring hospitalisation are defined as moderate.

If available, data on exacerbations occurring during the study will be summarised. This may include investigator defined exacerbations (including information on moderate or severe) and/or concomitant medication defined exacerbations. Concomitant medication defined exacerbations may be defined as treatment with systemic/oral corticosteroids and/or antibiotics where the exacerbation is deemed to have ended if no additional treatment with systemic/oral corticosteroids and/or antibiotics is required within < 7 days from the end of treatment for the primary exacerbation.

### **8.4.3. Population of Interest**

The secondary efficacy analyses will be based on the “All Subjects” population, unless otherwise specified.

#### **8.4.4. Statistical Analyses / Methods**

Details of the planned displays are provided in [Appendix 10: List of Data Displays](#) and will be based on GSK Data Standards and statistical principles.

Unless otherwise specified, endpoints / variables defined in Section 8.4.1 will be summarised using descriptive statistics, graphically presented (where appropriate) and listed.

### **9. RELATIONSHIP BETWEEN THE PHARMACODYNAMIC AND BIOMARKER DATA AND THE HRCT DATA**

#### **9.1. Relationship between the mRNA data and the HRCT data**

The relationship between a selection of the mRNA data and the HRCT data may be performed as an exploratory analysis. This may include scatter plots of individual participant data, linear regression lines, Pearson's correlation coefficient and 95% confidence intervals plots as appropriate. This data will be produced following SAC.

### **10. SAFETY ANALYSES**

The safety analyses will be based on the "All Subjects" population, unless otherwise specified.

#### **10.1. Adverse Events Analyses**

Adverse events analyses including the analysis of adverse events (AEs), Serious (SAEs) and other significant AEs will be based on GSK Core Data Standards. The details of the planned displays are provided in [Appendix 10: List of Data Displays](#).

#### **10.2. Clinical Laboratory Analyses**

Laboratory evaluations including the analyses of Chemistry laboratory tests, Haematology laboratory tests, Urinalysis, and liver function tests will be based on GSK Core Data Standards. The details of the planned displays are in [Appendix 10: List of Data Displays](#).

#### **10.3. Other Safety Analyses**

The analyses of non-laboratory safety test results including ECGs and vital signs will be based on GSK Core Data Standards, unless otherwise specified. The details of the planned displays are presented in [Appendix 10: List of Data Displays](#).

## **11. PHARMACOKINETIC ANALYSES**

### **11.1. Secondary Pharmacokinetic Analyses**

#### **11.1.1. Endpoint / Variables**

##### **11.1.1.1. Drug Concentration Measures**

Refer to [Appendix 5](#): Data Display Standards & Handling Conventions (Section [13.5.3](#) Reporting Standards for Pharmacokinetic)

##### **11.1.1.2. Derived Pharmacokinetic Parameters**

No non-compartmental analysis will be conducted for this study as such there will be no derived pharmacokinetic parameters.

#### **11.1.2. Summary Measure**

The concentrations of the samples will be summarised.

#### **11.1.3. Population of Interest**

The secondary pharmacokinetic analyses will be based on the “Pharmacokinetic” population, unless otherwise specified.

## **13. APPENDICES**

### **13.1. Appendix 1: Protocol Deviation Management**

#### **13.1.1. Important Protocol Deviations**

Based on an assessment of the important protocol deviations listed in the PDMP, partial data exclusions or time-point exclusions may occur which may not remove a subject from the analysis population, but may exclude a portion of the subject's data.

**13.2. Appendix 2: Schedule of Activities****13.2.1. Protocol Defined Schedule of Events****Screening and Follow Up Visits**

Procedure	Screening (up to 3 days prior to Visit 1)	Follow-up (7-14 days post-last dose)	Notes
Informed consent	X		
Demography	X		
Inclusion and exclusion criteria	X		
Full physical exam, including height and weight	X		
Brief physical examination, including weight		X	
Chest X-Ray	X		To be done before baseline HRCT to exclude significant pneumonia and other incidental serious underlying pathology.
Medical history (includes substance usage and Family history of premature CV disease)	X		Substances: Drugs, Alcohol, tobacco via history. No drug, alcohol screening is required.
Past and current medical conditions (including cardiovascular medical history and therapy history)	X		
Laboratory assessments (include Hematology and biochemistry) 	X	X	Historical values analysed by local lab to be used for eligibility assessment. Another sample must be collected and sent to central lab as soon as informed consent is obtained.
Hep B and Hep C screen 	X		
Urine pregnancy test (only WCBP)	X		Before conducting the HRCT. Done locally at the site.
12-lead ECG	X	X	Single assessment
Vital signs	X	X	Single assessment
HRCT (at TLC and FRC)	X		Within 48 h of diagnosis, if subject otherwise eligible. Includes electronic monitoring of breathing (if applicable). Baseline HRCT will be reviewed by the local site's radiologist to identify any significant occurring underlying medical conditions that require further clinical management or monitoring.

Procedure	Screening (up to 3 days prior to Visit 1)	Follow-up (7-14 days post-last dose)	Notes
Induced Sputum 	X 		To include sputum culture pre-first dose. Culture to be done by the local site laboratory.
Blood sample for mRNA Analysis	X 		Collected at any time on specified days
AE/SAE collection and review		X	
Concomitant medication review	X	X	

1. Due to the short screening window, central laboratory analysis results will not be available on time. Therefore, the local laboratory results should be used for eligibility assessment (to exclude severe subjects and underlying medical conditions). If local laboratory results are already available from diagnosis of current exacerbation, there is no need to take another sample for local analysis. A sample for central laboratory analysis should also be obtained. See Section 7.8.6 of Protocol Amendment 4 for further details.
2. If test otherwise performed within 3 months prior to first dose of study treatment, testing at screening is not required. Because of the short window for screening, treatment with GSK2269557 may start before receiving the result of the hepatitis tests. If subsequently the test is found to be positive, the subject may be withdrawn, as judged by the Principal Investigator in consultation with the Medical Monitor.
3. Induced sputum collection may be attempted on several occasions if an adequate sample is not produced at the first attempt.
4. To be collected at any time point before randomisation.

**Treatment Period**

Procedure	Treatment Period						Notes	
	Visit	1	2 	3	4	5		6
	Day	1	Within 48h / discharge	12	28	56		84
	Visit window	N/A	±1 days	±2 days	±2 days	- 4 / +2 days		- 4 / +2 days
SAFETY ASSESSMENTS								
AE/SAE collection and review	←=====→							
Concomitant medication review	←=====→							
Reliever usage	←=====→							
Brief physical exam, including weight	X 		X	X	X	X	Pre-dose	
Laboratory assessments (include haematology and biochemistry)	X 		X	X	X	X	Pre-dose	
12-lead ECG	X 		X	X	X	X	Pre-dose. Single assessment	
Vital signs	X 		X	X	X	X	Pre-dose. Single assessment	
Urine pregnancy test (only WCBP)			X	X			Before conducting the HRCT	
STUDY TREATMENT								
ELLIPTA™ Inhaler Training	X						Training conducted by reviewing the Patient Information Leaflet with the subject (no device will be used). Additional training may be conducted at the discretion of the investigator	
Randomisation	X							
Study drug administration	←=====→						Daily in the morning before breakfast, (with the exception of days when the subjects have a planned visit to the clinic. On those days, they will be dosed at the clinic).	
Assessment of study treatment compliance			X	X	X	X		
Diary Card dispense and review at clinic	X		X	X	X	X	Refer to SRM for details.	

Procedure	Treatment Period						Notes	
	Visit	1	2 	3	4	5		6
	Day	1	Within 48h / discharge	12	28	56		84
	Visit window	N/A	±1 days	±2 days	±2 days	- 4 / +2 days		- 4 / +2 days
EFFICACY ASSESSMENTS								
HRCT (at TLC and FRC)			X	X			At any time on specified days. Includes electronic monitoring of breathing (if applicable). The radiologist may review any of the scan(s) if they wish, but this is NOT required for the study. A formal review is required at screening only by the radiologist.	
FEV 1 and FVC	X	X	X	X	X	X	In clinic only for all visits where possible.	
PEF	←----->						Daily before drug administration at home. If subject in hospital, this may be collected using the handheld device provided prior to drug administration.	

OTHER ASSESSMENTS							
Blood sample for PK	X		X	X	X	X	Day 1: 5 min and 24 h post-dose. The 24 h post-dose time-point is optional for subjects not hospitalised. Pre-dose at all other time-points.
Sputum induction 			X	X		X	
Blood sample for mRNA analysis			X	X		X	
Genetic sample (PGx) 		X					Collected at any time after randomisation

1. On discharge if the subject was hospitalized. Within 48 hours of first dose administration if the subject was not hospitalised. See Section 4.2 of Protocol Amendment 4
2. Assessments do not need to be completed if screening assessments conducted within 48 hours
3. Induced sputum collection may be repeated on several occasions if an adequate sample is not produced at the first attempt
4. Informed consent for optional sub-studies (e.g. genetics research) must be obtained before collecting a sample. May be obtained at any visits.

### 13.3. Appendix 3: Assessment Windows

#### 13.3.1. Definitions of Assessment Windows for Analyses

Population	Target	Analysis Window		Analysis Timepoint
		Beginning Timepoint	Ending Timepoint	
Screening	NA	3 days prior to Visit 1 (Day 1)	Day 1	Screening
Safety, Efficacy, Study population and all other assessments	NA – Day of first dose	NA	NA	Visit 1
	If subject was hospitalised: Target = On discharge	Target -1 day	Target +1 day	Visit 2
	If subject wasn't hospitalised: Target = Within 48 hours of first dose administration			
	Day 12	Target -2 day	Target +3 day	Visit 3
	Day 28	Target -4 day	Target +2 day	Visit 4
	Day 56	Target -7 day	Target +6 day	Visit 5
	Day 84	Target -8 day	Target +4 day	Visit 6
Follow-up	NA	1 week following last day of dose	4 weeks following the last day of dose	Follow-up

## 13.4. Appendix 4: Study Phases and Treatment Emergent Adverse Events

### 13.4.1. Study Phases

Assessments and events will be classified according to the time of occurrence relative to the study treatment, unless otherwise specified

Study Phase	Definition
Pre-Treatment	Date ≤ Study Treatment Start Date
On-Treatment	Study Treatment Start Date < Date ≤ Study Treatment Stop Date
Post-Treatment	Date > Study Treatment Stop Date

#### 13.4.1.1. Study Phases for Concomitant Medication

Study Phase	Definition
Prior	If medication end date is not missing and is prior to screening visit
Concomitant	Any medication that is not a prior

#### NOTES:

- Please refer to [Appendix 7: Reporting Standards for Missing Data](#) for handling of missing and partial dates for concomitant medication. Use the rules in this table if concomitant medication date is completely missing.

### 13.4.2. Treatment States for Adverse Events

Flag	Definition
Pre-Treatment	
 
If AE onset date is before the treatment start date.
 
AE Start Date < Study Treatment Start Date
 

Treatment Emergent (On-Treatment)	
 
If AE onset date is on or after treatment start date & on or before treatment stop date.
 
Study Treatment Start Date ≤ AE Start Date ≤ Study Treatment Stop Date.
 

Post-Treatment	
 
If AE onset date is after the treatment stop date.
 
AE Start Date > Study Treatment Stop Date
 

Onset Time Since 1st Dose (Days)	
 
If Treatment Start Date > AE Onset Date, then Onset Time = AE Onset Date - Treatment Start Date
 
If Treatment Start Date ≤ AE Onset Date, then Onset Time = AE Onset Date - Treatment Start Date + 1
 
Missing otherwise.
 

Duration (Days)	
 
AE Resolution Date – AE Onset Date + 1
 

Drug-related	
 
If relationship is marked 'YES' on [Inform/CRF OR value is missing].
 

#### NOTES:

- If the study treatment stop date is missing, then the AE will be considered to be On-Treatment.
- Time of study treatment dosing and start/stop time of AEs should be considered, if collected.

### 13.5. Appendix 5: Data Display Standards & Handling Conventions

#### 13.5.1. Reporting Process

Software	

 
The currently supported versions of SAS software (version 9.4) will be used.
 
	
Reporting Area	
HARP Server	: UK1SALX00175.corpnet2.com
HARP Compound	: ARPROD/GSK2269557/mid201928 Note: the current planned reporting effort is final_01, this may be superseded.
Analysis Datasets	

 
Analysis datasets will be created according to Legacy GSK A&R dataset standards and Integrated Data Standards Library
 
	
Generation of RTF Files	

 
RTF files will be generated for all tables
 
	

#### 13.5.2. Reporting Standards

General	

 
The current GSK Integrated Data Standards Library (IDSL) will be applied for reporting, unless otherwise stated (IDSL Standards Location: https://spope.gsk.com/sites/IDSLLibrary/SitePages/Home.aspx):             
 
4.03 to 4.23: General Principles
 
5.01 to 5.08: Principles Related to Data Listings
 
6.01 to 6.11: Principles Related to Summary Tables
 
7.01 to 7.13: Principles Related to Graphics
 
 
 
Do not include subject level listings in the main body of the GSK Clinical Study Report. All subject level listings should be located in the modular appendices as ICH or non-ICH listings
 
A project wide decision was made to present GSK2269557 as Nemiralisib (abbreviated to NEMI) refer to Section 5.1 for further details.
 
	
Formats	

 
GSK IDSL Statistical Principles (5.03 & 6.06.3) for decimal places (DP's) will be adopted for reporting of data based on the raw data collected, unless otherwise stated.
 
Numeric data will be reported at the precision collected on the eCRF.
 
The reported precision from non eCRF sources will follow the IDSL statistical principles but may be adjusted to a clinically interpretable number of DP's.
 
	
Planned and Actual Time	

 
Reporting for tables, figures and formal statistical analyses:             
 
Planned time relative to dosing will be used in figures, summaries, statistical analyses and calculation of any derived parameters, unless otherwise stated.
 
The impact of any major deviation from the planned assessment times and/or scheduled visit days on the analyses and interpretation of the results will be assessed as appropriate.
 
 
 
Reporting for Data Listings:             
 
Planned and actual time relative to study drug dosing will be shown in listings (Refer to IDSL Statistical Principle 5.05.1).
 
Unscheduled or unplanned readings will be presented within the subject's listings.
 
 
 
	


 
• Visits outside the protocol defined time-windows (i.e. recorded as protocol deviations) will be included in listings but omitted from figures, summaries and statistical analyses.
 
	
Unscheduled Visits	

 
• Unscheduled visits will not be included in summary tables.
 
• Unscheduled visits will not be included in summary figures
 
• All unscheduled visits will be included in listings.
 
	
Descriptive Summary Statistics	
Continuous Data	Refer to IDSL Statistical Principle 6.06.1
Categorical Data	N, n, frequency, %
Graphical Displays	

 
• Refer to IDSL Statistical Principals 7.01 to 7.13.
 
• All graphics will be done using the SGPLOT/SGPANEL/SG template procedures
 
	

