## 5.2. Baseline Definitions

For all endpoints (except as noted in baseline definitions) the baseline value will be the latest pre-dose assessment with a non-missing value, including those from unscheduled visits. If time is not collected, Day 1 assessments are assumed to be taken prior to first dose and used as baseline.

Parameter	Study Assessments Considered as Baseline				Baseline Used in Data Display
	Screening	Day 1 (Pre-Treatment)	Day 2 Within 48H/discharge (On Treatment)	Day 12 (On Treatment)	
Safety					
Labs including Haematology	X	X			Day 1
ECG	X	X			Day 1
Vitals	X	X			Day 1
Efficacy					
HRCT Untrimmed	X				Screening
HRCT Scan Trimmed					
Screening&Day12	X				Screening
Screening&Day28	X				Screening
Day12&Day28				X	Day 12
FEV 1 and FVC		X	X		Day 1 
Daily PEF 		X			Day 1
					Mean of Days 1 to 3
					Maximum of Days 1 to 3
Pharmacodynamic					
Sputum and Blood	X				Screening
Genetic sample (PGx) 			X		

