### 13.6. Appendix 6: Derived and Transformed Data

#### 13.6.1. General

Multiple Measurements at One Analysis Time Point

 
• Mean of the measurements will be calculated and used in any derivation of summary statistics but if listed, all data will be presented.
 
• If there are two values within a time window (as per Section 13.3.1) the value closest to the target day for that window will be used. If values are the same distance from the target, then the mean will be taken.
 
• Participants having both High and Low values for Normal Ranges at any post-baseline visit for safety parameters will be counted in both the High and Low categories of “Any visit post-baseline” row of related summary tables. This will also be applicable to relevant Potential Clinical Importance summary tables.
 

Study Day

 
• Calculated as the number of days from First Dose Date:                         
 
• Ref Date = Missing → Study Day = Missing
 
• Ref Date < First Dose Date → Study Day = Ref Date – First Dose Date
 
• Ref Date ≥ First Dose Date → Study Day = Ref Date – (First Dose Date) + 1
 
 
 

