**13.10.6. Safety Tables**

Safety: Tables					
No.	Population	IDSL / Example Shell	Title	Programming Notes	Deliverable
Adverse Events (AEs)					
3.1.	All Subjects	AE1	Summary of All Adverse Events by System Organ Class and Preferred Term	ICH E3	SAC
3.2.	All Subjects	AE3	Summary of Common (>=5%) Adverse Events by Overall Frequency	ICH E3	SAC
3.3.	All Subjects	AE1	Summary All Drug-Related Adverse Events by System Organ Class and Preferred Term	ICH E3 Include flag for serious	SAC
3.4.	All Subjects	AE15	Summary of Common (>=5%) Non-serious Adverse Events by System Organ Class and Preferred Term (Number of Participant and Occurrences)	FDAAA, EudraCT	SAC
Serious and Other Significant Adverse Events					
3.5.	All Subjects	AE16	Summary of Serious Adverse Events by System Organ Class and Preferred Term (Number of Participants and Occurrences)	FDAAA, EudraCT	SAC
3.6.	All Subjects	AE1	Summary of Adverse Events Leading to Permanent Discontinuation of Study Treatment or Withdrawal from Study by System Organ Class and Preferred Term	IDSL	SAC
Laboratory: Chemistry					
3.7.	All Subjects	LB1	Summary of Chemistry	ICH E3	SAC

Safety: Tables					
No.	Population	IDSL / Example Shell	Title	Programming Notes	Deliverable
3.8.	All Subjects	LB15	Summary of Worst Case Emergent Laboratory Chemistry Results Post-Baseline Relative to Baseline		SAC
Laboratory: Hematology					
3.9.	All Subjects	LB1	Summary of Hematology	ICH E3	SAC
3.10.	All Subjects	LB15	Summary of Worst Case Emergent Laboratory Hematology Results Post-Baseline Relative to Baseline		SAC
Laboratory: Hepatobiliary (Liver)					
3.11.	All Subjects	LIVER1	Summary of Liver Monitoring/Stopping Event Reporting	IDSL	SAC
3.12.	All Subjects	LIVER10	Summary of Hepatobiliary Laboratory Abnormalities	IDSL	SAC
ECG					
3.13.	All Subjects	EG1	Summary of ECG Findings	IDSL	SAC
3.14.	All Subjects	EG2	Summary of ECG Values by Visit		SAC
3.15.	All Subjects	EG2	Summary of Change from Baseline in ECG Values by Visit	IDSL	SAC
Vital Signs					
3.16.	All Subjects	VS1	Summary of Vital Signs		SAC

Safety: Tables					
No.	Population	IDSL / Example Shell	Title	Programming Notes	Deliverable
3.17.	All Subjects	VS1	Summary of Change from Baseline in Vital Signs	ICH E3 Includes Baseline Values	SAC
3.18.	All Subjects	VS7	Summary of Worst Case Vital Sign Results Relative to Potential Clinical Importance (PCI) Criteria Post-Baseline Relative to Baseline		SAC

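### Section 13.5.2 keeps unscheduled visits out of every summary table, with no exception for the worst-case and abnormality safety tables (3.8, 3.10, 3.12, 3.18), so their counts can be understated

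*SAP*

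**What the plan says.** The reporting standards in SAP section 13.5.2 contain a short block on unscheduled visits. For tables it reads "Unscheduled visits will not be included in summary tables". A parallel line says the same for summary figures, and a third reads "All unscheduled visits will be included in listings". The amended RAP and the original RAP bound with it carry the same block, so this is current text.

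Section 13.10.6 of the amended RAP plans four tables that look for extremes or abnormalities rather than visit means:

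- Table 3.8, "Summary of Worst Case Emergent Laboratory Chemistry Results Post-Baseline Relative to Baseline"
- Table 3.10, "Summary of Worst Case Emergent Laboratory Hematology Results Post-Baseline Relative to Baseline"
- Table 3.12, "Summary of Hepatobiliary Laboratory Abnormalities"
- Table 3.18, worst-case vital signs judged against the limits of potential clinical importance (PCI)

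The programming notes for 3.8, 3.10 and 3.18 are blank, and the note for 3.12 only names the sponsor's display standard.

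Two other sections bear on the point. Section 5.2 takes as baseline the last non-missing value before dosing, "including those from unscheduled visits". Section 13.6.1 says that a subject with both High and Low safety values over the visits after baseline is counted in both categories of an any-visit row, and it extends this to the PCI tables. The same section says that where two values share an analysis window, "the value closest to the target day for that window will be used".

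**The concern.** A worst-case table exists to show the most extreme post-baseline value each subject had. If the table program first drops every unscheduled visit, the result is the worst scheduled value. A subject whose only out-of-range laboratory or vital-sign result came from an unscheduled test would count as having no shift or no PCI value, while the PCI listings (25, 26, 32 and 33) would show that result.

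Safety and tolerability against placebo is a secondary objective (section 2.2). Section 5.1 presents the safety summaries in four separate device-by-treatment columns. The columns are small, so a single subject is visible in the percentages.

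**Working it through.** **Does the exclusion reach these four tables?** Section 13.5.2 speaks of summary tables without qualification, and Tables 3.8, 3.10, 3.12 and 3.18 are summary tables. No section or programming note exempts them. The sponsor's library standard cannot supply an exemption by default, because section 13.5.2 gives it effect only where the plan is silent: "The current GSK Integrated Data Standards Library (IDSL) will be applied for reporting, unless otherwise stated". The exclusion is a case where the plan does state otherwise.

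**Direction.** Let S be a subject's scheduled post-baseline values and U the unscheduled ones. The worst value over S cannot be worse than the worst value over S and U together. Restricting the table to S therefore leaves a subject's category unchanged or makes it look better. Counts can be too low and never too high.

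**Consistency with 13.6.1.** The any-visit row counts values over any visit after baseline, while 13.5.2 removes some of those visits. Neither section refers to the other, so two programmers could build the row differently and each claim to follow the plan.

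**Consistency with 5.2.** An unscheduled value can enter before dosing, as baseline, but cannot enter after dosing, as the worst case. A table that compares the two draws them from differently filtered data.

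**Could the analysis windows bring the values back in?** Section 13.5.2 excludes unscheduled visits whether or not they fall in a window. The windows would not suffice in any case. From the offsets in section 13.3.1 of the amended RAP:

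- Day 12, −2/+3: Days 10–15
- Day 28, −4/+2: Days 24–30
- Day 56, −7/+6: Days 49–62
- Day 84, −8/+4: Days 76–88

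The days between windows are 16–23 (8 days), 31–48 (18) and 63–75 (13), and 8 + 18 + 13 = 39. From Day 12 to Day 84 there are 84 − 12 + 1 = 73 days, so 39 of 73 belong to no window. This leaves aside Visit 2, which is tied to discharge or 48 hours and has no scheduled laboratory or vital-sign assessment.

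**What one subject is worth.** The SAP states no figure on this point, so there is none to reproduce. Section 2.3 gives 28 subjects randomised 1:1 on Diskus and about 45 planned in total.

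- Diskus: 28 / 2 = 14 per arm; 1/14 = 7.1 percentage points
- Ellipta: 45 − 28 = 17, so 8 or 9 per arm; 1/9 = 11.1 and 1/8 = 12.5 percentage points

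These figures show the weight of one subject in a column. They do not estimate how many subjects are affected.

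**The case against.** The strongest reply is that the plan does not settle the matter as firmly as section 13.5.2 alone suggests. The any-visit rule in 13.6.1 is specific to safety, while 13.5.2 is a general display convention. Sections 10.2 and 10.3 base the laboratory and vital-sign analyses on the sponsor's core standards, and the four tables point to shells (LB15, LIVER10, VS7) that are not in the document. Those shells may use all post-baseline values. This stands in part: what the programs would do cannot be known from the SAP. But a visit in 13.6.1 may also mean a scheduled visit, and 13.5.2 puts the plan's own statements ahead of the library. The explicit text still says to exclude.

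It also stands that no data are lost. Unscheduled results go to the listings for a study of about 45 subjects. Adverse events are classified by date rather than visit, and Table 3.11 counts liver events.

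A reader might infer more than the document supports:

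- **That the worst values are mostly found at unscheduled repeats, so toxicity is understated.** The SAP gives no data on this. If a repeat follows an abnormal scheduled value, that subject is already counted, and the repeat matters only if it moves the subject to a worse category. The clear loss is an unscheduled abnormal value in a subject whose scheduled values are all normal.
- **That the closest-to-target rule in 13.6.1 makes the loss worse.** It selects one value per time point. Once unscheduled visits are out, there is usually only one scheduled value per window and the rule has little to act on.
- **That the difference from section 5.2 is itself an error.** The last available pre-dose value is a reasonable baseline. The difference shows uneven handling and no more.
- **That the comparison with placebo is biased.** The rule applies equally to all arms, and nothing in the SAP shows a distortion between them.

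**Conclusion.** The point holds in a limited form. As written, section 13.5.2 makes Tables 3.8, 3.10, 3.12 and 3.18 blind to post-baseline values recorded only at unscheduled visits. That sits badly with what these tables are for and conflicts with the any-visit rule in 13.6.1. The direction is certain: understatement or no change.

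The size is unknown and may be nil, because the SAP gives no rate of unscheduled testing. The figures for one reclassified subject rest on an even split within each cohort and on the planned total of about 45. The defect lies in the summary counts and not in the availability of the data. Leaving unscheduled visits out of by-visit summaries is sound and should stay.

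**What to change.** In section 13.5.2, limit the exclusion to by-visit summaries and figures. State that Tables 3.8, 3.10, 3.12 and 3.18, and any any-visit post-baseline row, use all post-baseline values, scheduled and unscheduled, including unscheduled values on days that belong to no analysis window.

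In section 13.6.1, state that the closest-to-target and mean rules select values for by-visit summaries only. Without this, those rules could remove an extreme value once unscheduled values are admitted.

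The cost is a few sentences of SAP text and a changed filter in four programs. Abnormality counts may rise and cannot fall. If the intention was only to keep unscheduled visits from appearing as table rows, the same wording makes that clear.
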